9.1.2. Alopecia Density and Extent Score (ALODEX)

The ALODEX score is a measurement of the amount of scalp with hair loss (Olsen, submitted). The Investigator will calculate the ALODEX score using the iPAD provided by Aclaris at Baseline (Visit 2), Day 29 (Visit 7) and as detailed in Section 7.3 for subjects who continue in the open-label extension. Equipment, supplies, training and a detailed Reference Guide will be provided to the investigational site prior to the initiation of subject enrollment.

9.2. Pharmacodynamic (Biomarker) Assessment

9.2.1. Scalp Biopsy (PD)

A 4-mm punch biopsy of the scalp will be obtained on Baseline (Visit 2) just prior to the first application of study medication and at Day 29 (Visit 7) 24 hours (\pm 30 minutes) after the study medication application for histology and RNA sequencing (APPENDIX 5). At Visit 13, a 4-mm biopsy will be obtained approximately 24 hours \pm 30 minutes after the morning dose on the day prior to the visit.

9.2.2. Blood for Immunologic Evaluation (T-cells)

The blood samples will be obtained on Day 1 (Visit 2) predose and on Day 29 (Visit 7) 24 hours (\pm 30 minutes) after the study medication application for measurement of the following tests including:

- T, B, NK lymphocytes, CD4 $^{+}$, CD8 $^{+}$ T-cells
- T-regulatory and T-cell subtypes
- RNA seq
- TCR seq

At Visit 13, blood samples will be obtained approximately 24 hours \pm 30 minutes after the morning dose on the day prior to the visit.

9.3. Pharmacokinetic Assessment

9.3.1. Scalp Biopsy (PK)

A 4-mm punch biopsy of the scalp will be obtained on Day 2 (Visit 3) and on Day 29 (Visit 7) 24 hours (\pm 30 minutes) after the study medication application (on Day 1/Visit 2 and Day 28/Visit 6) to determine the concentration of ATI-50002 in the skin (APPENDIX 5). The scalp biopsy should be obtained after the area of the scalp to be biopsied is tape stripped using 5 D-Squame circular discs.

The bioanalytical lab will provide instructions on the collection and shipment of samples for analysis.

9.3.2. Blood Samples (Double-blind Period)

For the first six subjects enrolled into the study, blood samples for PK analysis of ATI-50002 will be collected by a qualified staff member. On Baseline/ Day 1 (Visit 2) and Day 28 (Visit 6) blood samples will be collected at predose (0-hour) (just prior to study medication application in the morning) and then at the following times **after study medication application**:

- 1 hour (\pm 5 minutes)
- 2 hours (\pm 10 minutes)
- 4 hours (\pm 10 minutes)
- 8 hours (\pm 10 minutes)

On Day 2 (Visit 3) and Day 29 (Visit 7)

- 24 hours (\pm 30 minutes)

The bioanalytical laboratory will provide instructions on the collection and shipment of samples.

9.4. Eyebrow Assessments (Open-Label Extension)

Subjects with eyebrow loss in one or both eyebrows will be allowed to treat their affected eyebrow(s) during the open-label period of the study. Both the investigator and subject will assess eyebrow loss at entry into the open-label extension and then monthly for the first 6 months, then at 9 and 12 months during the open-label treatment period. The Investigator will document the affected areas of the eyebrow or brow(s) on the source document and eCRF.

9.4.1. Clinician's Eyebrow Assessment (CEA) (Open-Label Period)

The CEA is the Investigator's assessment of the affected eyebrow(s) at a particular point in time. The Investigator should NOT refer to any other assessments to assist with these assessments.

At Visits 8 - 16, the Investigator will assess the affected eyebrow(s) using the scale below and report the one integer that best describes the amount of eyebrow hair present. **If both eyebrows are affected, each eyebrow will be assessed separately.**

Clinician's Eyebrow Assessment

Grade	Descriptor
0	No eyebrow hair: No terminal hairs are visible in the affected area(s)
1	A little eyebrow hair: Occasional terminal hairs are visible in the affected area(s)
2	Some eyebrow hair: Numerous terminal hairs are visible in the affected area(s)
3	Most eyebrow hair: Mostly complete eyebrow regrowth with terminal hair in the affected area(s)
4	Full eyebrow hair: Complete eyebrow regrowth with terminal hair in the affected area (s)

9.4.2. Subject's Eyebrow Assessment (SEA) (Open-Label Period):

The SEA is the subject's assessment of the appearance of eyebrow hair present on the affected eyebrow(s) at a particular point in time. The subject should NOT refer to any other assessments to assist with these assessments.

At Visits 8-16, the subject will assess the affected eyebrow(s) using the scale below and report the one integer that best describes the amount of eyebrow hair present. **If both eyebrows are affected, each eyebrow will be assessed separately.**

Subject's Eyebrow Assessment

Grade	Descriptor
0	No eyebrow hair: No thick, coarse hairs are visible in the affected area(s)
1	A little eyebrow hair: A few thick, coarse hairs are visible in the affected area(s)
2	Some eyebrow hair: Numerous thick, coarse hairs are visible in the affected area(s)
3	Most eyebrow hair: The majority of the affected area(s) of the eyebrow is covered in thick, coarse hairs
4	Full eyebrow hair: The affected area(s) of the eyebrow is fully covered in thick, coarse hairs

An investigational staff member will identify the eyebrow to be evaluated by the subject, educate the subject on the SEA scale before each evaluation and direct the subject to assess the eyebrow, one eyebrow at a time. The staff member should not influence the subject's assessment.

The study staff member will report the SEA grade the subject indicates in the source document for the affected eyebrow(s). Both the subject and the study staff member must sign/initial the source document to indicate the subject performed the SEA as instructed.

9.5. Assessment of Safety

Safety will be assessed throughout the study by the investigator or a designated and appropriately trained staff member.

9.5.1. Vital signs

Vital signs will be measured at each visit during the study. The following items will be measured:

- Body temperature
- Pulse rate
- Respiration rate
- Blood pressure (systolic and diastolic) after the subject sits quietly for at least 5 minutes
- Height and Weight (at Visit 2 only).

Any measure that is, in the opinion of the investigator, abnormal AND clinically significant (CS) must be recorded as medical history if found prior to the first study medication application, or as an AE if found after the first study medication treatment begins.

A systolic blood pressure >140mm Hg or a diastolic blood pressure >90 mmHg is considered abnormal and therefore must be defined as CS or not clinically significant (NCS) on the eCRF. A weight >300 lbs. is considered abnormal and therefore must be defined as CS or NCS on the eCRF.

9.5.2. Physical Examination

The investigator or designee will perform a physical examination for all body systems (general appearance, examination of head, eyes, ears, nose and throat, respiratory, cardiovascular, abdominal, extremities, neurological, musculoskeletal, lymphatic and skin assessment) at Screening (Visit 1) and Day 29 (Visit 7). For subjects who are enrolled in the Open-label extension, a physical examination will also be performed at Week 56 (Visit 16).

9.5.3. Clinical Laboratory Assessments

A qualified staff member will collect non-fasting samples for clinical laboratory analysis at the times in the visit schedule in Section 7.3. Samples will be sent to a central laboratory for analysis. Refer to the study specific laboratory manual for handling and shipping instructions.

The following tests will be conducted:

Chemistry Panel	Complete Blood Count
Albumin	Hematocrit
Alkaline phosphatase	Hemoglobin
Alanine aminotransferase (ALT)	Platelet count
Aspartate aminotransferase (AST)	Red blood cell morphology
Blood urea nitrogen (BUN)	Red blood cell count
Bicarbonate	White blood cell count
Calcium	White blood cell differential
Chloride	% & absolute
Creatinine	Basophils
Glucose	Eosinophils
Lactate dehydrogenase (LDH)	Lymphocytes
Phosphorus	Monocytes
Potassium	Neutrophils
Sodium	
Total bilirubin	
	Urinalysis

Chemistry Panel	Complete Blood Count
Total protein	
Uric acid	
HDL, LDL, Total cholesterol,	
Triglycerides	

Screening Tests Only

Hep B, HCV, HIV
Quantiferon Gold
Total Iron Binding Capacity (TIBC)
Serum iron
Serum Ferritin
T3/T4, TSH
Serum Pregnancy

The results of the clinical laboratory tests will be reported on the central laboratory's standard reports. The investigator must note NCS or CS to define the clinical relevance of any result that is outside the normal range for the laboratory. The investigator must date and initial every laboratory report.

The investigator or subinvestigator must review all the Screening (Visit 1) laboratory test results against the study entry criteria for each subject prior to Baseline (Visit 2). The investigator must report all laboratory results that are BOTH outside the normal range for the laboratory AND, in the opinion of the investigator, CS as medical history if found prior to the first study medication treatment or as an AE if found after the first study medication treatment begins. The investigator must review all laboratory reports in a timely manner.

9.5.4. Pregnancy tests

Subjects who are WOCBP must have a negative serum pregnancy test result at Screening (Visit 1) to continue in the study, a negative UPT at Baseline (Visit 2) **prior to randomization** and **prior to study medication application** at Day 28 (Visit 6). WOCBP who are enrolled in the open label period will have UPT at the visits detailed in Section 7.3 during the treatment period. The UPT kits provided by Aclaris Therapeutics, Inc. have a minimum sensitivity of 25-mIU β -HCG/milliliter (mL) of urine. If the result of any post-treatment UPT is positive, the subject will be withdrawn from the study and the subject's pregnancy documented and followed.

9.5.5. ECGs

Standard 12-lead ECGs will be performed by a qualified staff member at Screening (Visit 1), Baseline (Visit 2), Day 15 (Visit 5), Day 29 (Visit 7) and the visits outlined in Section 7.3. The ECGs must be obtained using a standard 12-lead ECG with a 10mm/mV amplitude, at 25mm/sec and a 5-10-second duration. To ensure a steady heart rate the subject must rest quietly in the supine position for at least 5 minutes prior to performing the ECG.

A central lab, eResearchTechnology, Inc. (ERT), will provide equipment, supplies and site training. In addition, ERT will process ECGs received by the sites and report results via a secure study portal. The ECG results will be interpreted by a qualified health professional (evaluator) and

the interpretation reported either directly on the tracing or in a separate report. The evaluator will interpret the results of every ECG and define the ECG as “normal” or “abnormal”. Variations such as minor ST changes (*i.e.*, <0.5mm depression) and early re-polarization are considered normal.

The investigator must review the evaluator’s interpretation of each subject’s screening ECG prior to Baseline (Visit 2). The investigator will review the evaluator’s interpretation of all ECG reports in a timely manner and comment on the clinical relevance of any result that is defined by the evaluator as abnormal.

Any abnormalities that are, in the opinion of the investigator, clinically significant, must be reported as medical history if found prior to the start of the first study medication application or as an AE if found after the start of the first study medication application (see Section 10.1.1).

9.6. Other Assessments

9.6.1. Demographics, Medical History and Alopecia Areata History

During the Screening visit, the investigator or designee will interview each subject to obtain demographic information including date of birth, sex at birth, Fitzpatrick Skin Type, race and, if appropriate, ethnicity. The investigator or designee will interview each subject to obtain medical history information related to all medical conditions, surgeries and disease states that, at Screening (Visit 1): are ongoing, require concomitant therapy or are, in the opinion of the investigator, relevant to the subject’s study participation. In addition, the medical history of women who are not of childbearing potential should reflect the reason *e.g.* post-menopausal for 1 year or greater, bilateral tubal ligation, or hysterectomy. The investigator or designee will also obtain an extensive AA history at Screening (Visit 1) (APPENDIX 3).

9.6.2. Photographic Assessment

A qualified investigational staff member will take standardized photographs of the scalp at Baseline (Visit 2), prior to study medication application, Visit 7 (Day 29) prior to the scalp biopsy and if enrolled in the open-label extension at the visits detailed in Section 7.3. The photographs are to document the baseline hair loss and any early signs of hair growth during treatment. Equipment, supplies, training and detailed instructions for obtaining and managing photographs will be provided to the investigational center prior to the initiation of subject enrollment.

10. ADVERSE EVENTS

Adverse events will be monitored throughout the study and reported on the appropriate Aclaris Therapeutics, Inc. AE eCRF.

10.1. Definitions

10.1.1. Adverse Events (AE)

An AE is any untoward medical occurrence in a subject or clinical investigation subject administered a study medication(s) and which does not necessarily have a causal relationship with

the study medication. An AE can therefore be any unfavorable and unintended sign or symptom associated with the use of a study medication (including an abnormal laboratory finding), whether or not related to the study medication.

Thus, any new, clinically significant worsening of an existing sign, symptom or disease, should be considered an AE.

Every new episode or clinically significant worsening of a chronic condition (e.g., headaches, seasonal allergies, depression, or hypertension) should be reported as a separate AE, even if the condition is reported in the subject's medical history.

The investigator should, when certain, report a diagnosis rather than the signs, symptoms or clinically significant abnormal laboratory values associated with the AE. Otherwise, signs, symptoms or abnormal laboratory values may be used to describe the AE.

Any CS abnormality discovered prior to the first study medication treatment should be reported as medical history, not as an AE.

10.1.2. Serious Adverse Event (SAE)

A Serious Adverse Event is any untoward medical occurrence that at any dose:

- Results in death
- Is life threatening
- Requires inpatient hospitalization or prolongation of existing hospitalization
- Results in persistent or significant disability/incapacity, or
- Is a congenital anomaly/birth defect
- Is an important medical event

The term "life threatening" refers to an event in which the subject was at risk of death at the time of event; it does not refer to an event that hypothetically might have caused death if it were more severe.

Inpatient hospitalization is considered to have occurred if the subject is admitted to the hospital on an in-patient basis, even if released the same day. Prolongation of hospitalization is defined as an additional night stay in the hospital. Hospitalization for a diagnostic test (even if related to an AE) or elective hospitalization that was planned before study enrollment (signing the ICF) are not themselves reasons for an event to be defined as a SAE.

Important medical events are those that may not be immediately life threatening, result in death or hospitalization, but are clearly of major clinical significance and may jeopardize the subject or require intervention to prevent one of the outcomes listed in the SAE definition above. These should also usually be considered serious. Examples of such events are intensive treatment in an emergency room or at home for allergic bronchospasm, blood dyscrasias or convulsions that do not result in hospitalization.

10.1.3. Unexpected Adverse Event

An AE is considered unexpected if it is not listed in the Investigator Brochure or is not listed at the specificity or severity that has been observed.

10.1.4. Adverse Event Reporting Period

The investigator must start reporting non-serious AEs with the subject's first study medication application and continue reporting until the end of the subject's last study visit. Reporting for SAEs must start when the subject signs the ICF and continue until the end of the subject's last visit.

10.1.5. Severity

The investigator is to define the severity of each AE using the following definitions as a guideline. The investigator will consider the range of the possible severity of the event and identify the severity that is the most appropriate according to her/his medical judgment.

Mild – Awareness of signs or symptom, but easily tolerated.

Moderate – Discomfort, enough to cause interference with usual activity.

Severe – Incapacitating with inability to perform usual activity.

10.1.6. Relationship to Study Medication

The investigator will determine if there is a reasonable causal relationship between the study medication and an AE or not. The investigator will use her/his best medical judgment and consider all relevant factors (*e.g.*, temporal relationship, location of the event, the subject's relevant medical history, concomitant therapies and concurrent conditions) to determine the relationship of the AE to the study medication. The investigator will define the relationship of an AE to the study medication by selecting one of the following categories:

Related – There is a reasonable causal relationship between the study medication and the AE.

Not Related – There is not a reasonable causal relationship between the study medication and the AE.

The expression “reasonable causal relationship” is meant to convey in general that there are facts (evidence) or arguments to suggest a causal relationship (International Conference on Harmonization [ICH] E2A).

10.2. Reporting Procedures

10.2.1. Procedures for Reporting Adverse Events

At each post-enrollment visit, the investigator will question the subject to elicit AEs using a non-directive question such as “Has there been any change in your health since the previous study visit?” If appropriate, based on the subject's response to non-directed questioning to elicit AEs, the investigator will follow-up with directed questions and appropriate evaluations.

Any AE noted during the reporting period must be reported in the source documents and on the appropriate AE eCRF. AEs that are defined as “Not Related” to the study medications will be followed until they are resolved or until the subject’s last study visit. AEs that are defined as “Related” to the study medications will be followed until they are resolved or, if not resolved after the subject’s last study visit, until in the opinion of the investigator, the AE reaches a clinically stable outcome with or without sequelae.

10.2.2. Procedure for Reporting a Serious Adverse Event

Upon becoming aware of a SAE occurring during the AE reporting period, whether or not related to the study medications, the investigator must:

1. Take the appropriate medical action to ensure the subject’s safety.

Immediately (within 24 hours) inform the Medical Monitor of the SAE by telephone:

[name], RAC
Aclaris Therapeutics, Inc.
[name]
[name]
[name]
Office [contact]
SAE [contact]
E-mail: [contact]

2. Within 24-hours complete, as fully as possible, an AE eCRF and an SAE form; fax or e-mail the forms and any other relevant information (e.g., concomitant medication eCRF, medical history eCRF, laboratory test results) to the Aclaris Therapeutics, Inc. Medical Monitor.
3. Monitor and document the progress of the SAE until it resolves or, if not resolved after the subject’s last study visit, until in the opinion of the investigator the AE reaches a clinically stable outcome with or without sequelae AND the investigator and Aclaris Therapeutics, Inc. Medical Monitor agree that the SAE is satisfactorily resolved.
4. Inform the Aclaris Therapeutics, Inc. Medical Monitor of SAE updates by telephone followed by an SAE form update sent by e-mail.
5. Comply with the appropriate regulatory requirements and Aclaris Therapeutics, Inc. instructions regarding reporting of the SAE to the responsible Institutional Review Board (IRB) or Ethics Committee (EC).

10.2.3. Safety Monitoring ECG Discontinuation Criteria

Any subject who develops any of the following ECG criteria during the active treatment phase will be instructed to stop study medication and will be withdrawn from the study:

- A post-study medication ECG result where the evaluator’s interpretation shows any of the following:
 - Clinically significant rhythm disturbance other than sinus rhythm or ectopic supraventricular rhythm (ectopic atrial rhythm)

- Clinically significant conduction disturbance including PR >240msec, pre-excitation (delta wave and PR <120msec), second degree or higher AV block
- New finding of QRS>120ms (if not present at screen. For example, subjects with Right Bundle Branch Block at screening would not need to be withdrawn from the study if their subsequent ECGs remained unchanged).
- Evidence of QT-interval prolongation, defined as an increase in the QTcF interval >60ms from Visit 1
- New QTcF > 500 ms
- Acute signs of ischemia or infarction
- Any ECG abnormality which may, in the opinion of the investigator, represent a new medical issue of concern

10.2.4. Study Medication Interruption and Discontinuation

10.2.4.1 Study Medication Interruption

Treatment with ATI-50002 Topical Solution should be temporarily interrupted in the event of severe adverse events considered related to ATI-50002, or in the event of one or more of the abnormal laboratory values in Table 2.

Table 2: Study Medication Interruption Criteria

Laboratory Test	Hold Study Medication if:	Resume Study Medication if:
WBC count	< 2 x 10 ⁹ /L	≥ 2.5 x 10 ⁹ /L
ANC	< 1 x 10 ⁹ /L	≥ 1.5 x 10 ⁹ /L
Lymphocyte count	< 0.5 x 10 ⁹ /L	≥ 0.75 x 10 ⁹ /L
Platelet count	< 75 x 10 ⁹ /L	≥ 100 x 10 ⁹ /L
Hemoglobin	< 8 g/dL or decrease > 2 g/dL	≥ 10 g/dL
AST or ALT	> 3 x ULN	< 2 x ULN or within 20% of baseline values
Serum creatinine	>2 x ULN	<1.5 x ULN or within 10% of baseline value

If a subject has one or more of the abnormal laboratory values noted in Table 2, the investigator or designee upon receipt and review of the central laboratory report should instruct the subject to interrupt study medication applications. The investigator or designee should ask the subject about symptoms, concomitant illnesses and medications and repeat the test(s) as soon as possible. The Medical Monitor must be notified of dose interruptions due to SAEs considered related to study medication or laboratory abnormalities noted in Table 2.

If the retest confirms the abnormal laboratory value, then the study medication interruption should continue, followed by repeat testing once a week or sooner at the discretion of the investigator. The subject should be followed until the laboratory abnormality(s) return to normal or to baseline values. Study medication can be resumed after the abnormal lab value returns to normal or baseline, if in the opinion of the Investigator, it is in the best interest of the subject to continue.

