8. History of, current or suspected systemic or cutaneous malignancy and/or lymphoproliferative disease, other than subjects with a history of adequately treated and well healed and completely cleared non-melanoma skin cancers (basal or squamous cell carcinoma) treated successfully at least 1 year prior to study entry with no evidence of disease.
9. Evidence of active or latent bacterial (including tuberculosis) or viral infections at the time of enrollment, or history of incompletely treated or untreated tuberculosis. Subjects who have completed therapy for latent tuberculosis may participate.
10. History of a serious local infection (e.g., cellulitis, abscess) or systemic infection including but not limited to a history of treated infection (e.g., pneumonia, septicemia) within 3 months of baseline (Visit 2). Subjects on an antibiotic for a non-serious, acute local infection must complete the course prior to enrollment into the study.
11. Positive for HIV, Hepatitis B or C. Subjects with serologic evidence of Hepatitis B vaccination (HepB surface Ab without the presence of HepB sAg) will be allowed to participate.
12. Herpes zoster or cytomegalovirus (CMV) that resolved less than 2 months before study enrollment. Subjects with a history of frequent outbreaks of Herpes Simplex Virus (defined as 4 or more outbreaks a year).
13. Clinically significant laboratory abnormalities at screening that, in the opinion of the Investigator, would make the subject a poor candidate for the study.
14. Subjects with absolute neutrophil count <1,000/mm³, or platelet count <50,000/mL.
15. Subject unable to comply with the following required washout periods:

Therapy/Medication	Washout Period
Systemic Therapies	
Disease Modifying Anti-Rheumatic Drugs (DMARDs), Biologics or immunosuppressants, such as: anakinra, adalimumab, azathioprine, corticosteroids, cyclosporine, etanercept, infliximab, methotrexate, TNF inhibitors, ustekinumab	1 month or 5 half-lives whichever is greater
Plaquenil	2 months
JAK inhibitors (oral or topical)	Prior or current treatment with a JAK inhibitor is prohibited at any time
Intralesional Steroids on the Scalp	1 month

	
Topical Treatments on the Scalp
 
Anthralin, bimatoprost, corticosteroids, diphenycprone, diphenylcycloprophenone (DPCP), Squaric acid dibutylester (SADBE), minoxidil, pimecrolimus, tacrolimus
	1 month
	Phototherapy, Laser Therapy, Excimer Laser	3 months

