10. History of a serious local infection (*e.g.*, cellulitis, abscess) or systemic infection including but not limited to, history of treated (*e.g.*, pneumonia, septicemia) within 3 months prior to baseline (Visit 2). Subjects on an antibiotic for a non-serious, acute local infection must complete the course prior to enrollment into the study.
11. Positive for HIV, Hepatitis B or C. Subjects with serologic evidence of Hepatitis B vaccination (HepB surface Ab without the presence of HepB sAg) will be allowed to participate.
12. Herpes zoster or cytomegalovirus (CMV) that resolved less than 2 months before study enrollment. Subjects with a history of frequent outbreaks of Herpes Simplex Virus (defined as 4 or more outbreaks a year).
13. Clinically significant laboratory abnormalities at screening that, in the opinion of the Investigator, would make the subject a poor candidate for the study.
14. Subjects with absolute neutrophil count $<1,000/\text{mm}^3$ or platelet count $<50,000/\text{mL}$.
15. Subject unable to comply with the following required washout periods:

Therapy/Medication	Washout Period
Systemic Therapies	
Disease Modifying Anti-Rheumatic Drugs (DMARDs), Biologics or immunosuppressants, such as: anakinra, adalimumab, azathioprine, corticosteroids, cyclosporine, etanercept, infliximab, methotrexate, TNF inhibitors, ustekinumab	1 month or 5 half-lives whichever is greater
Plaquenil	2 months
	Prior or current treatment with a JAK inhibitor is prohibited at any time.

Therapy/Medication	Washout Period
Systemic Therapies	
JAK inhibitors (oral or topical)	
Intralesional Steroids on the Scalp	1 month
Topical Treatments on the Scalp	
Anthralin, bimatoprost, corticosteroids, diphenycprone, diphenylcycloprophenone (DPCP), Squaric acid dibutylester (SADBE), minoxidil, pimecrolimus, tacrolimus	1 month
Phototherapy, Laser Therapy, Excimer Laser	3 months

16. Participation in an investigational drug or device trial in which administration of an investigational drug or device occurred within 30 days or 5 half-lives (whichever is longer) of Screening (Visit 1). Subjects having participated in a study of an investigational drug, device or biologic agent for alopecia areata (AA, AU, AT) within 1 year of screening will be eligible to participate only with individual permission from the Medical Monitor.
17. Sensitivity to any of the ingredients in the study medications.

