6.7. Replacement Subjects

Subject enrollment will continue until approximately 12 subjects have been randomized. Subjects who are randomized and do not complete the study will not be replaced.

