10.2.4.2 Study Medication Discontinuation

Study medication should be permanently discontinued in the event of any of the following:

- Severe infection requiring parenteral antimicrobial therapy or hospitalization
- Symptomatic herpes zoster
- Malignancy – except for non-melanoma skin cancer (e.g. squamous or basal cell carcinoma) not in or near the treatment area
- Anaphylactic or severe allergic reaction
- WBC Count: $< 1 \times 10^9/L$ or second occurrence of $< 2 \times 10^9/L$
- ANC: $< 0.5 \times 10^9/L$ or second occurrence of $< 1 \times 10^9/L$
- Lymphocyte count: $< 0.3 \times 10^9/L$ or second occurrence of $< 0.5 \times 10^9/L$
- Platelet count: $< 50 \times 10^9/L$ or second event of $< 75 \times 10^9/L$ - in each case, value should be confirmed by retesting before treatment discontinuation
- Hemoglobin: $< 6.5 \text{ g/dL}$ or second occurrence of $< 8 \text{ g/dL}$ - in each case, value should be confirmed by retesting before treatment discontinuation
- AST or ALT:
 - $> 5 \times \text{ULN}$ persisting for 1 week of study medication interruption or second event of $> 5 \times \text{ULN}$
 - $> 3 \times \text{ULN}$ with total bilirubin $> 2 \times \text{ULN}$ or symptoms of hepatocellular injury (fatigue, nausea, vomiting, right upper quadrant pain or tenderness, fever, rash and/ or eosinophilia ($> 5\%$)).
- Serum creatinine: $> 2 \times \text{ULN}$ persisting for > 2 weeks of treatment discontinuation or second occurrence of $> 2 \times \text{ULN}$

The continued treatment of subjects who experience other serious or severe adverse events considered related to study treatment should be discussed with the Sponsor's medical monitor.

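### The platelet limit for entry lies below the protocol's own hold limit, so a subject can be eligible and already meet the hold rule with no change from baseline

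*Protocol*

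**What the plan says.** **Entry.** Exclusion 14 in the protocol synopsis reads "Subjects with absolute neutrophil count <1,000/mm³, or platelet count <50,000/mL". Section 6.4 repeats the same numbers and units. Exclusion 13 adds a judgement-based bar: "Clinically significant laboratory abnormalities at screening that, in the opinion of the Investigator, would make the subject a poor candidate for the study".

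**Hold.** Section 10.2.4.1 interrupts treatment "in the event of one or more of the abnormal laboratory values in Table 2". Table 2 gives the platelet limit as below 75 × 10⁹/L, with resumption at 100 × 10⁹/L or more. The text under the table gives a different route back: "Study medication can be resumed after the abnormal lab value returns to normal or baseline", provided the investigator thinks continuing is in the subject's best interest.

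**Permanent stop.** Section 10.2.4.2 stops treatment for a platelet count below 50 × 10⁹/L, or for a second event below 75 × 10⁹/L, in each case confirmed by retest. It does not define a second event.

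**Consequence for numbers.** The synopsis plans 8 active and 4 vehicle subjects. Section 6.7 states: "Subjects who are randomized and do not complete the study will not be replaced".

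**The concern.** An entry limit and an on-treatment hold limit for the same test should fit together: a value good enough to start treatment should not, unchanged, be a reason to interrupt it. Here the platelet entry limit is the lower of the two. Even on the lenient reading of its unit, it equals the permanent-stop limit.

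A subject in the overlap could be randomized, apply study medication, and then be held for a count that was present before the first application. The trial is small, safety and tolerability belong to its primary objective, and lost subjects are not replaced. A hold or stop before Day 28 would also break the planned Day 29 sampling, which is timed 24 hours after a Day 28 application. After premature discontinuation, Section 6.8 seeks only the Visit 16 assessments, and in the Section 7.3 schedule these include no PK or PD biopsy.

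**Working it through.** The plan gives no figure to reproduce. The check is to put every limit on one scale and run an unchanged value through the rules.

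**Unit conversion**
- Platelets, if per microlitre was meant: 50,000 × 10⁶ per L = 50 × 10⁹/L.
- Platelets, as printed per mL: 50,000 × 10³ per L = 0.05 × 10⁹/L.
- ANC: 1,000/mm³ × 10⁶ per L = 1.0 × 10⁹/L.

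**Limits side by side (× 10⁹/L)**

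| Test | Eligible if | Hold if | Resume (Table 2) | Permanent stop |
|---|---|---|---|---|
| Platelets, per microlitre | ≥50 | <75 | ≥100 | <50, or second event <75 |
| Platelets, as printed | ≥0.05 | <75 | ≥100 | <50, or second event <75 |
| ANC | ≥1.0 | <1.0 | ≥1.5 | <0.5, or second occurrence <1.0 |

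**A stable platelet count of 60**
1. Entry: 60 ≥ 50, so exclusion 14 does not apply. The pre-Baseline review in Section 9.5.3 compares screening results with the entry criteria, not with Table 2.
2. Hold: 60 < 75, so the rule is met. Section 7.3 schedules laboratory samples at Day 1 and Day 15, and the hold is given when the central laboratory report is reviewed. The first application can therefore come before it.
3. Resume under Table 2: 60 < 100, so the subject stays on hold.
4. Resume under the text below the table: 60 is the baseline value, so resumption is open to the investigator. The next 60 is again below 75. If that counts as a second event and is confirmed by retest, treatment stops permanently.

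The same sequence applies to any unchanged count from 50 to <75, under either reading of the unit.

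**A stable platelet count from 0.05 to <50, unit as printed.** Exclusion 14 does not apply, and the count is below 50. It meets the permanent-stop limit directly once confirmed by retest, with no second event needed.

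**ANC.** The entry and hold limits coincide at 1.0. An unchanged value of 1.0 or more meets neither hold nor stop, so there is no margin but no overlap.

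**Other Table 2 tests.** WBC, lymphocytes, hemoglobin, AST/ALT and creatinine have no numeric entry limit, so no entry figure conflicts with the table.

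**Baseline exemptions elsewhere.** Section 10.2.3 spares a subject whose QRS finding was present at screening and is unchanged. Table 2's resume values for AST/ALT and creatinine refer to baseline. The platelet rows and bullets contain neither kind of clause.

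**Size.** One affected subject is 1/8 = 12.5% of the active arm or 1/4 = 25% of the vehicle arm.

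**The case against.** **Clinical judgement would screen such a subject out.** Inclusion 7 requires good general health, exclusion 7 bars severe or uncontrolled hematological disease, and exclusion 13 covers clinically significant screening results. In practice these may well catch a count of 60. They are discretionary, however, and two sites could apply them differently. They make the case rarer without removing the conflict between the printed figures.

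**The permanent stop is not inevitable.** This stands. A reader might infer that a stable count of 60 leads from hold to permanent stop. That requires the sentence below Table 2 to override the table's ≥100 value, a count that never moved to be treated as having returned to baseline, the investigator to choose resumption, and an unchanged low count to qualify as a second event. Table 2 mentions baseline for AST/ALT and creatinine but not for platelets, which favours the reading that the subject simply stays on hold. Treatment is still lost on that reading.

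**The problem does not extend across the blood counts.** This also stands. A reader might see ANC of 1.0 to <1.5 × 10⁹/L as a second overlap because it lies below Table 2's resume value. A resume value applies only after a hold, and these subjects would not have been held. Leaving the remaining tests to judgement is a design choice, not a contradiction.

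**The safety results are largely protected.** A reader might infer that baseline-driven holds would pass for drug effects in the safety tables. SAP Section 4.4 sets the laboratory baseline at the last value on or before first application, and Section 4.4.5 reports shifts and changes from it, so an unchanged low count appears as low to low. Protocol Section 9.5.3 records clinically significant findings from before treatment as medical history. The SAP plans no table of laboratory interruptions. What remains is mainly disposition (SAP Section 4.1.2), where a stop would be listed with its reason.

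**Conclusion.** The conflict is real and confined to platelets. On the protocol's own figures, a stable count of 50 to <75 × 10⁹/L is eligible and meets the hold rule with no change from baseline, whichever unit was meant. Whether it then meets the permanent-stop rule depends on two unresolved points: which resume rule governs, and what a second event is. If the unit is taken as printed, eligible counts below 50 × 10⁹/L meet the permanent-stop limit directly after retest.

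The documents give no frequency for such counts. They should be rare, and the 12.5% and 25% figures are what one such subject would represent, not an expected loss. The conclusion assumes that the discretionary criteria do not exclude the subject. The likely harm is avoidable loss of treatment and of Day 29 PK and PD data, with some effect on disposition, and not a material distortion of the laboratory safety analysis. The point is worth correcting because the trial is small, has no replacement, and the correction is cheap.

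**What to change.** The sponsor's medical team should reconcile the platelet limits and unit in exclusion 14 (synopsis and Section 6.4), Table 2 and Section 10.2.4.2, so that a platelet count accepted at entry does not by itself meet a hold or stop rule. The same revision should settle Table 2's resume column against the sentence below it and say what counts as a second event. Which limit moves, or whether an exemption for an unchanged baseline value like the QRS one in Section 10.2.3 is used, is for the sponsor to decide. No rule is needed here for ANC or the other Table 2 tests.

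The cost is protocol wording and possibly an occasional extra screen failure; platelets are already measured at screening. If enrollment is complete, the sponsor can still check whether any subject's baseline platelet count was below 75 × 10⁹/L and flag it in the listings.
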